3.1.3 Medical history

Medical history and current medical conditions will be summarized using FAS, by dose cohorts of Phase I and by group of Phase II and will also be listed. Separate summaries will be presented for current and past medical conditions; these summaries will be presented by primary system organ class and preferred term. Medical history/current medical conditions will be coded using Medical Dictionary for Regulatory Activities (MedDRA) terminology.

3.1.4 Diagnosis and extent of cancer

For the patients in FAS, the summary statistics will be provided for the following variables for diagnosis and extent of cancer: Diagnosis of disease

- Histological grades
- Staging system used
- Stage at initial diagnosis
- Stage at study entry
- Histological grade
- Predominant histology/cytology
- Number and type of metastatic sites involved.
- Time since initial diagnosis

Time since initial diagnosis will be summarized in months. A month is defined as $365.25/12=30.4375$ days. This data will also be categorized into time intervals. Frequency counts and percentages will be presented for the number of patients in each interval. The summary will be by dose cohorts of Phase I and by group of Phase II.

3.1.5 Other baseline characteristics

ER, PgR and HER2, Rb status, prior line of endocrine therapy and chemotherapy prior CDK4/6 inhibitor and duration of CDK4/6 inhibitor will also be summarized and listed using FAS, by dose cohorts of Phase I and by group of Phase II.

3.1.6 Prior, concomitant and post therapies

Concomitant medications and significant non-drug therapies prior to (within 30 days prior to first dose) and after the start of the study drug treatment will be listed by patient and summarized by ATC (Anatomical Therapeutic Chemical Classification System) term. All prior and

concomitant medication/significant non-drug therapies entered into the database will be coded using the World Health Organization (WHO) Drug Reference List dictionary, which is supplied by Novartis and used by CRO at the time of coding.

These summaries will include medications starting on or after the start of study treatment or medications starting prior to the start of study treatment and continuing after the start of study treatment. Any prior concomitant medications or significant non-drug therapies starting and ending prior to the start of study treatment will be listed.

The number and percentage of patients taking such treatments will be summarized for patients in the Safety Set, by dose cohorts of Phase I and by group of Phase II.

3.1.7 Prior antineoplastic therapy

Prior anti-neoplastic therapy will be listed in three separate listings: (i) medications, (ii) radiotherapy, and (iii) surgery. This summary will be provided for FAS patients by dose cohorts of Phase I and by group for Phase II.

The summary of prior anti-neoplastic medication will include the total number of regimens used at last therapy, setting of last medication, and also the time from last medication to progression, the best response at last therapy. Best Response is defined as the best recorded patient response during all previous treatment regimens, up to and including the last recorded.

The last medication is defined taking into account the end date.

All prior antineoplastic medications will also be tabulated by ATC code, preferred term by dose cohorts of Phase I and by group for Phase II.

The summary of prior anti-neoplastic radiotherapy will include a summary of radiotherapy locations, including all locations recorded for each patients. Setting, method and prior radiotherapy of bone marrow (Y/N) at last radiotherapy will also be summarized.

The summary of prior anti-neoplastic surgeries will include the time between the last surgery to start of treatment, procedure applied in last surgery and residual disease at last surgery.

A summary of post discontinuation antineoplastic medications, surgeries and radiotherapies will also be provided with recorded details.

3.2 Treatments (study treatment, rescue medication, concomitant therapies, compliance)

3.2.1 Study treatment exposure

The following algorithm will be used to calculate the duration of study treatment exposure (in cycles and in days) for patients who takes at least 1 dose of the study treatment:

- Duration of exposure (days) to investigational drug = date of last administration of the study drug – date of first administration of the study drug + 1.

- Duration of exposure (days) to study treatment = (latest of last dates of exposure to study treatment (ribociclib, everolimus and exemestane)) – (date of first administration of study treatment (ribociclib, everolimus and exemestane)) + 1.

For patients who did not take any drug, the duration of drug exposure is by definition equal to zero.

- Cumulative Dose: Cumulative dose is defined as the total dose given to a patient during the study treatment. For patients who did not take any drug the actual cumulative dose is by definition equal to zero.
- Average Daily Dose: It is defined cumulative dose divided by the number of days the patients took the drug (excludes the no-dose period)
- Dose Intensity (DI): DI is defined as the ratio of cumulative dose and the number of days the patient should have taken the drug (includes the no-dose period).
- Planned dose intensity (PDI): PDI is defined as the ratio of total planned dose and the number of days the patient should have taken the drug [(planned dose * (last dose date – first dose date+1))].
- Relative Dose Intensity (RDI): RDI is defined as the ratio of dose intensity (DI) and planned dose intensity (PDI) based on planned dose and planned duration, expressed as percentage.

Cumulative Dose, average daily dose, DI, PDI and RDI will be calculated separately for each of the component of study treatment.

Additionally, prior duration of CDK4/6 against the duration of CDK4/6 during the study will be summarized by 25th, 50th (median) and 75th Percentiles of duration.

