***Note: There are no restrictions as to which endocrine therapy patients received as their last line of therapy just prior to randomization.**

8. Patients who received up 3 lines of therapy for advanced breast cancer are allowed. This includes a maximum of 1 line of chemotherapy and a maximum of 3 lines of endocrine therapy in the advanced setting so long as the patient has not received more than a total of 3 lines of therapy. Patients must have recovered to grade 1 or better from any adverse events (except alopecia and/or neuropathy) related to previous therapy prior to starting study treatment.

Note: If patient relapsed with documented evidence of progression on/or within 12 months from completion of adjuvant endocrine therapy, then this is considered one line of therapy.

9. Patients previously treated on any CDK 4/6 inhibitor (i.e. ribociclib, abemaciclib OR palbociclib) must have:
 - Remained on treatment for ≥ 4 months for advanced breast cancer or metastatic disease prior to progression, AND
 - Progressed on, or within 30 days following the discontinuation of a CDK 4/6 inhibitor.

Phase II Only:

- Patients must have progressed on only one CDK 4/6 inhibitor. A CDK 4/6 inhibitor must have been the last treatment regimen prior to starting study treatment.

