2.1 Data analysis general information

Data will be analyzed by Novartis and/or the designated Contract Research Organization (CRO), according to the data analysis section of the study protocol. Any data analysis carried out independently by the investigator must be submitted to Novartis before publication or presentation. Data from all participating centers will be combined so that an adequate number of patients are available for analysis.

All statistical analyses will be performed using SAS® Version 9.4.

The planned statistical analysis is described in Section 10 of the protocol (Appendix 16.1.1 of the CSR). Data will be summarized with respect to demographic and baseline characteristics, efficacy and safety observations.

The study data will be analyzed and reported based on all patients' data up to the time when all patients have potentially completed at least six cycles of treatment or discontinued the study. Any additional data for patients continuing to receive study treatment past the data cutoff date for the primary CSR will be reported once all patients have discontinued the study or at the end of the study, whichever occurs first.

Data will be summarized and listed by dose groups. For safety end point, all patients will be analyzed for each phase and may be pooled for analysis. The efficacy data will be analyzed for Phase I and Phase II of this study separately.

Categorical data will be presented as frequencies and percentages. For continuous data, mean, standard deviation, median, 25th and 75th percentiles, minimum, and maximum will be presented.

Screen failure patients are those who signed the informed consent, but never started the study treatment for any reason. For these patients, the eCRF data collected, will not be included in any analysis, but will be reported in the CSR as separate listings.

The reason for discontinuation from study will be summarized and listed, along with dates of first and last study drug treatment, duration of exposure to study drug treatment and date of discontinuation for each patient. Other missing data will simply be noted as missing on appropriate tables/listings.

Unless otherwise specified, all statistical tests will be performed at a two-sided significance level of 0.05 and confidence intervals will be calculated with 95% confidence.

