6.1 Imputation rules

6.1.1 Study drug

In the calculation of treatment exposure duration, if a dosing record has either a missing end date (for the last record for that treatment component) or an end date after the cut-off date, the cut-off date will be used as the end date. Such imputed data will be flagged in the listings. Where a date is recorded as a partial date, the missing day will be imputed as follows:

Start date: The day will be imputed by the 15th of the month. If day and month are missing day and month will be imputed by July 1st of the year. If there is a record indicating that the dose record started earlier, the start date will be imputed by the end date of the previous record + 1 day. In case the imputed start date is later than the complete end date, the record will not be considered for analysis.

End date: The day will be imputed by the 15th of the month, and if day and month are missing then by July 1st of the year. If there is a record indicating that this started later, the end date will be imputed by the start date of the next record - 1 day. In case the imputed end date is earlier than the complete start date, the record will not be considered for analysis.

Imputed DAR start and end dates will be flagged in the listings.

The protocol allows for continuous dosing record entry with start dates and end dates for all compounds of study treatment. A separate dosing record should be entered whenever there is a

change in the dosing which can be due to dose change, delay or missed doses. If the start date and end date is on the same date then that DAR record will be called single dose DAR record.

For dates known to be within the trial period, the last known contact date will be used if this imputation makes the date later than the last known contact date but within the trial completion date. If the imputed date is earlier than the first medication date, the first medication date will be used.

For dates prior to the treatment start, the treatment start date will be used if this imputation makes the date later than the treatment start date.

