6.4.2 Time to event analysis

The following variables will be used:

- Progression, Survival, Definitive deterioration: Event
- Censoring indicator variable: 1=Censored; 0=Event

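### Prior versus on-study CDK4/6 inhibitor duration is summarized by plain percentiles, which shortens the upper on-study percentile at the primary cut-off and sets it beside prior durations that are at least 4 months by eligibility

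*SAP*

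**What the plan says.** SAP 3.2.1 (Study treatment exposure) adds one line to the exposure summaries: "prior duration of CDK4/6 against the duration of CDK4/6 during the study will be summarized by 25th, 50th (median) and 75th Percentiles of duration". The on-study quantity is not defined separately. I take it to be ribociclib exposure, since the same section sets "Duration of exposure (days) to investigational drug = date of last administration of the study drug" minus the first administration date plus one day, and SAP 2.1.1.1 identifies the study drug as ribociclib.

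SAP 6.1.1 covers a last dosing record with no end date, or with an end date past the cut-off: "the cut-off date will be used as the end date". The imputed date is flagged in listings, but nothing marks the duration as incomplete in a summary.

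SAP 6.4.2 confines survival methods to four endpoints: "For analyzing PFS, OS and DOR, TDD, PROC LIFETEST SAS® procedure will be used for Kaplan Meier plots". Treatment duration is not among them.

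On timing, SAP 2.1 places the primary analysis on data "up to the time when all patients have potentially completed at least six cycles of treatment or discontinued the study". Data from patients who continue beyond that "will be reported once all patients have discontinued the study or at the end of the study, whichever occurs first".

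On the prior side, inclusion criterion 9 (Protocol 5.2) requires a previously treated patient to have stayed on the CDK4/6 inhibitor for at least 4 "months for advanced breast cancer or metastatic disease prior to progression", with progression on it or within 30 days of stopping. Phase I also admits patients who never had a CDK4/6 inhibitor.

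**The concern.** The two durations are not measured on the same footing. Each prior duration is complete, because the earlier inhibitor had been stopped, and none is below 4 months. On-study durations have no lower limit, and some are unfinished at the cut-off yet enter as if they had ended.

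The trial's rationale (Protocol 2.1) is that keeping CDK4/6 inhibition going after progression may still help. A reader will naturally use this summary to ask how on-study treatment time compares with the previous course. Both features work against the on-study side of that comparison, through different mechanisms and with different reach.

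**Working it through.** The documents give no figure for this summary, so there is nothing to reproduce. The check concerns direction and size.

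**Inputs from the documents**
- Minimum time since first dose for anyone still on drug at the primary cut-off: 6 cycles × 28 days = 168 days = 168/30.4375 = 5.52 months (SAP 2.1; month length from SAP 3.1.4).
- Planned Phase II accrual: 12 months (Protocol synopsis).
- Design alternative: 30% clinical benefit at 24 weeks (SAP 4).
- Minimum follow-up at end of study: 15 months after last enrolment (Protocol 4.3).
- Floor on prior duration: 4 months (Protocol 5.2, criterion 9).

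**Assumptions**
- Durations are exponential.
- Accrual is uniform.
- Clinical benefit at 24 weeks stands in for still being on drug at 168 days.

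**Step 1: which percentiles can move.** Every observed duration below 168 days is a true one. A percentile whose true value lies below 168 days is therefore unaffected by the cut-off. The 75th percentile is affected only if more than 25% are on drug at 168 days, the median only if more than 50% are, and the 25th only if more than 75% are.

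**Step 2: by how much.** Let s be the share on drug at 168 days and λ = −ln(s)/5.52 per month. The true percentile is −ln(1−p)/λ. Follow-up is uniform from 5.52 to 17.52 months. Beyond 5.52 months, the plain 75th percentile x therefore solves exp(−λx) × (17.52 − x)/12 = 0.25.
- s = 30%: λ = 0.218. True value 1.386/0.218 = 6.4. At x = 6.12, 0.263 × 0.950 = 0.25, so the table prints 6.1.
- s = 50%: λ = 0.1256. True value 1.386/0.1256 = 11.0. At x = 8.62, 0.339 × 0.742 = 0.25, so the table prints 8.6.

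Simulation agrees (months):

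| On drug at 168 days | True 25th/50th/75th | Printed 25th/50th/75th | Ongoing at cut-off |
|---|---|---|---|
| 30% | 1.3 / 3.2 / 6.4 | 1.3 / 3.2 / 6.1 | 11% |
| 50% | 2.3 / 5.5 / 11.0 | 2.3 / 5.5 / 8.6 | 26% |
| 60% | 3.1 / 7.5 / 15.0 | 3.1 / 6.5 / 10.0 | 36% |

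With accrual spread over 24 months, the 75th percentile prints as 6.2 (30%) and 9.6 (50%), so the effect is smaller.

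**Step 3: the later report.** With at least 15 months of follow-up, plain and true quartiles agree within 0.1 month up to 60% on drug at 24 weeks. At 70%, only the 75th percentile still differs (17.7 against 21.5). SAP 1.1.2 still describes 12 months after first dose. At 50% the conclusion holds under that too, since 11.0 is below 12.

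**Step 4: the 4-month floor.** For an exponential duration, conditioning on at least 4 months adds 4 months to every percentile. Quartiles of 2.5/6/12 become 6.5/10/16. This acts only on the prior column and does not fade with follow-up.

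**The case against.** The strongest reply is that this is a descriptive line in an exposure section, with no test, threshold or decision attached. Exposure accrued up to a cut-off is a legitimate quantity to report. Durability is handled properly elsewhere: PFS and DOR use Kaplan-Meier, a swimmer plot shows treatment length (SAP 3.7.2.2), and disposition tables count ongoing patients (SAP 3.1.1.1). All of that stands and keeps the point minor.

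At the design rate of 30%, the 25th percentile and median are untouched and the 75th loses about 0.3 month. That also stands. The 50% case is not far-fetched: the Amendment 2 rationale reports 50% clinical benefit at 6 months among Cohort A patients who had progressed on a CDK4/6 inhibitor. But Cohort A had only 8 evaluable patients in all.

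Uniform 12-month accrual fits Group 1 poorly. By 22 May 2017, 45 Phase II patients were already enrolled, before Cohort C opened. Group 1 therefore has longer follow-up, and the shortening would fall more on Group 2.

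The layout is also unsettled. The sentence could mean a cross-summary by quartile of prior duration, and the table shells are in a separate document. On either layout, the ongoing on-study durations still enter as complete.

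A reader might go further and infer that on-study duration will look falsely short throughout, or that the 4-month floor makes the table understate it. The documents do not support either. Only percentiles beyond 168 days can be shortened. The floor lengthens the prior column, whose values are the enrolled patients' actual durations, and leaves the on-study column unchanged.

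**Conclusion.** The point holds in limited form. Followed as written, the plan treats unfinished ribociclib courses as completed. At the primary cut-off this shortens on-study percentiles beyond 168 days, chiefly the 75th: by about 0.3 month if 30% are on drug at 24 weeks and by about 2.4 months (11.0 − 8.6) if 50% are. The median moves only above 50% on drug at 168 days. Most of the shortening is gone by the end-of-study report.

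The 4-month eligibility floor is a separate matter of comparability. It tilts the comparison against on-study duration at every percentile and at every cut, but it introduces no error into the on-study figures.

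The 168-day threshold follows from the SAP. The sizes rest on the exponential, uniform-accrual and proxy assumptions. Since the summary is descriptive, this is an improvement to make and does not threaten the trial's conclusions.

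**What to change.** In SAP 3.2.1 and 6.4.2, state that the on-study ribociclib duration percentiles are estimated by Kaplan-Meier, with patients still on ribociclib at the cut-off censored there. Show the number ongoing by Phase I cohort and Phase II group. Limit the comparison to patients with a prior CDK4/6 inhibitor, because CDK4/6-naive Phase I patients have no prior duration. Footnote that prior durations are at least 4 months by eligibility.

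Do not try to equalize the columns by restricting on-study percentiles to patients who reached 4 months. That conditions on a post-treatment outcome and removes early failures: at the 30% rate, 1 − exp(−0.218 × 4) = 58% of patients under the exponential assumption.

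The cost is a few SAP sentences and one more PROC LIFETEST call on data already collected. The downside is that an upper percentile may be reported as not reached.

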3.2.2 Study treatment

The actual dose and duration (days) of ribociclib, everolimus and exemestane will be summarized by means of descriptive statistics. The summary data will be presented by dose cohorts of Phase I and by group of Phase II. The total daily doses of ribociclib, everolimus and exemestane for each patient will be summarized using descriptive statistics (e.g. mean, median, maximum and minimum doses). The exposure data for all the patients will be provided based on the Safety Set.

3.2.3 Dose change or interruptions

The number of patients who have dose change or interruptions and the reasons for such change/interruptions will be summarized by study treatment component using Safety Set. This summary will be provided by dose cohorts of Phase I and by group of Phase II.

If a patient moves from a protocol-studied dose down to a lower-than-protocol-studied dose or to the dose level being studied under the protocol but on a less frequent regimen, such changes will then be counted as reductions.

3.2.4 Compliance

Compliance to the protocol will be assessed by the number and proportion of patients with protocol deviations for all patients in FAS. These will be identified prior to database lock and will be listed and summarized by dose cohorts of Phase I and by group for Phase II.

Compliance to the study drug will be assessed by the number of dose reductions and dose interruptions for all patients in FAS.

3.3 Efficacy Evaluations

3.3.1 Disease assessment

Disease assessment will be carried out in patients by radiological assessments (e.g. CT /MRI/bone scan).

All the components of the disease assessment will be listed. These components will be further assessed based on the responses provided by the Investigator on centrally and locally assessed data. The response assessment by Investigator should be based on all available data as per RECIST V1.1 guidelines.

Patients should have at least one documented measurable lesion (per RECIST v1.1) or in the absence of measurable disease, have at least one lytic or mixed (blastic/lytic) bone lesion at study entry.

Table 3-1 Response criteria for target lesions

| Response Criteria | Evaluation of target lesions |
|---------------------------|--|
| Complete Response (CR): | Disappearance of all non-nodal target lesions. In addition, any pathological lymph nodes assigned as target lesions must have a reduction in short axis to <10 mm ¹ |
| Partial Response (PR): | At least a 30% decrease in the sum of diameter of all target lesions, taking as reference the baseline sum of diameters. |
| Progressive Disease (PD): | At least a 20% increase in the sum of diameter of all measured target lesions, taking as reference the smallest sum of diameter of all target lesions recorded at or after baseline. In addition to the relative increase of 20%, the sum must also demonstrate an absolute increase of at least 5 mm ² . |
| Stable Disease (SD): | Neither sufficient shrinkage to qualify for PR or CR nor an increase in lesions which would qualify for PD. |
| Unknown (UNK) | Progression has not been documented and one or more target lesions have not been assessed or have been assessed using a different method than baseline. ³ |

¹. SOD for CR may not be zero when nodal lesions are part of target lesions

². Following an initial CR, a PD cannot be assigned if all non-nodal target lesions are still not present and all nodal lesions are <10 mm in size. In this case, the target lesion response is CR

³. Methodology change See CSP Section 14.2.6.

Table 3-2 Response criteria for non-target lesions

| Response Criteria | Evaluation of non-target lesions |
|---------------------------|---|
| Complete Response (CR): | Disappearance of all non-target lesions. In addition, all lymph nodes assigned a non-target lesions must be non-pathological in size (<10 mm short axis) |
| Progressive Disease (PD): | Unequivocal progression of existing non-target lesions. ¹ |
| Non-CR/Non-PD: | Neither CR nor PD |
| Unknown (UNK) | Progression has not been documented and one or more non-target lesions have not been assessed or have been assessed using a different method than baseline. |

¹. Although a clear progression of non-target lesions only is exceptional, in such circumstances, the opinion of the treating physician does prevail and the progression status should be confirmed later on by the review panel (or study chair).

Table 3-3 Overall lesion response at each assessment

| Target lesions | Non-target lesions | New Lesions | Overall lesion response |
|-----------------------|----------------------------|--------------------|--------------------------------|
| CR | CR | No | CR ¹ |
| CR | Non-CR/Non-PD ³ | No | PR |
| CR, PR, SD | UNK | No | UNK |
| PR | Non-PD and not UNK | No | PR ¹ |
| SD | Non-PD and not UNK | No | SD ^{1, 2} |
| UNK | Non-PD or UNK | No | UNK ¹ |
| PD | Any | Yes or No | PD |
| Any | PD | Yes or No | PD |
| Any | Any | Yes | PD |

¹. This overall lesion response also applies when there are no non-target lesions identified at baseline.

². Once confirmed PR was achieved, all these assessments are considered PR.

³. As defined in CSP Section 14.2.8.

If there are no baseline scans available at all, then the overall lesion response at each assessment should be considered Unknown (UNK).

If the evaluation of any of the target or non-target lesions identified at baseline could not be made during follow-up, the overall status must be ‘unknown’ unless progression was seen. Further details can be found in Protocol Appendix 2.

